10 RISK / BENEFIT ASSESSMENT

- **10.1** Anticipated risks. Describe the reasonably foreseeable risks of harm, discomforts, and hazards to the subjects and others of the research procedures. For each harm, discomfort, or hazard:
 - Describe the magnitude, probability, duration, and/or reversibility of the harm, discomfort, or hazard, AND
 - Describe how you will manage or reduce the risks.
 - Consider physical, psychological, social, legal, and economic risks, including risks to financial standing, employability, insurability, educational advancement or reputation.
 - Examples of "others": embryo, fetus, or nursing child; family members; a specific group.
 - Do not include the risks of non-research procedures that are already being performed.
 - If the study design specifies that subjects will be assigned to a specific condition or intervention, then the condition or intervention is a research procedure even if it is a standard of care.
 - Examples of mitigation strategies: inclusion/exclusion criteria; applying appropriate data security measures to prevent unauthorized access to individually identifiable data; coding data; taking blood samples to monitor something that indicates drug toxicity.
 - As with all questions on this application, you may refer to uploaded documents.

There are minimal risks associated with participation in this study. Any potential risks that might exist fall into three categories: (1) risks associated with the intervention; (2) risks associated with research assessments (3) risks associated with potential loss of confidentiality. We address each in turn below.

1. Risks of the intervention. mHealth interventions for people with SSD have not been shown to cause harm in any of our mHealth studies or in research reported in the published literature. Our extensive line of FOCUS research in similar CMHC settings suggests it is a highly acceptable and safe intervention in this environment. We have deployed FOCUS for periods ranging five days to seven months and have not had any adverse events reported. PI [name] is currently conducting a separate smartphone intervention study with more high-risk participants who were recently discharged from the hospital as part of a relapse prevention program for schizophrenia (R01MH103148). The four-year study is concluding in July 2017; participants with SSD have been using a smartphone system (CrossCheck) that is deployed for a period that is four times longer than what is proposed for the current study. The CrossCheck platform is much more elaborate and technologically complex than the FOCUS intervention we propose to use here. Similar to the FOUCS line of research, we have not had any adverse events reported.

Participants in FOCUS research choose if/ when to engage. The main risk is engaging in intervention content while engaged in other activities that require participants' full attention (e.g., driving, crossing streets, operating machinery or appliances, caring for a child). Participants will be instructed to use the smartphone only when it is completely safe to do so. Participants will be socialized to the intervention model and advised that research staff and project personnel (i.e., facilitators) will not see their intervention use content or messages in any time-sensitive manner and that these forms of communication should not be used for an emergency.

- 2. Risks associated with research assessments. Research assessments include questions about functioning, psychiatric symptoms, other emotional or social problems, and illness management and recovery skills (patients) as well as evaluation of FOCUS usefulness and assessment of its strengths and limitations in the context of CMHC workflow (for staff). Responding to these items may cause discomfort or distress in some. CMHC staff may feel apprehensive about offering feedback that may be viewed as critical of FOCUS intervention. Individuals may also endorse suicidal ideation when completing measures or bring this up during screenings or debriefings.
- 3. Risks associated with potential loss of confidentiality. Whenever healthcare information is relayed outside of the physical clinic it creates new patient privacy and data security challenges. Potential risks

include loss, theft, or inadequate disposal of a mobile phone that contains health information, unauthorized access to information while it is stored on the device or transmitted (intentionally or inadvertently). There is also the remote possibility that research records will be subpoenaed for civil or criminal proceedings. All of these potential losses of confidentiality will be disclosed in the informed consent documents

4. Risks associated with disclosure of harm to self or others. There is a possibility of participants disclosing harmful intentions. If participants disclose suicidal or homicidal intention, research staff will probe for more details (i.e. if they have a plan, date, person of interest), and will deliberate with the lead PI (a trained clinical psychologist) the level of risk and if there is a need for clinical response. Unless there is an overt need for immediate care (i.e., participant said they would immediately hurt themselves or others, admitted to overdosing prior to meeting with research staff, etc). If elevation is deemed necessary by the research team, a member of the research staff would then reach out to their clinical team to proceed with the outlined protocol procedures of the local site (mental health clinic serving as a study site). If participants indicate a 1 or higher on Q9 of the PhQ9 Scale ("Thoughts that you would be better off dead, or of hurting yourself"), will be sent an email providing additional resources (please see 'Email for PHQ9' attachment in this modification).

10.2 Unforeseeable risks. Are there any research procedures that may have risks that are currently unforeseeable?

Example: using a drug that hasn't been used before in this subject population.

X	No	
	Ye	→ If yes, identify the procedures.
	S	

10.3 Subjects who will be under regional or general anesthesiology. Will any research procedures occur while subjects-patients are under general or regional anesthesia, or during the 3 hours preceding general or regional anesthesia (supplied for non-research reasons)?

	or regional anesthesia (supplied for non-research reasons)?
x No Yes	→ If yes, check all the boxes that apply.
	Administration of any drug for research purposes
	Inserting an intra-venous (central or peripheral) or intra-arterial line for research purposes
	Obtaining samples of blood, urine, bone marrow or cerebrospinal fluid for research purposes
	Obtaining a research sample from tissue or organs that would not otherwise be removed during surgery
	Administration of a radio-isotope for research purposes**
	Implantation of an experimental device

Other manipulations or procedures performed solely for research purposes (e.g., experimental liver dialysis, experimental brain stimulation)

If you checked any of the boxes:

You must provide the name and institutional affiliation of a physician anesthesiologist who is a member of your research team or who will serve as a safety consultant about the interactions between your research procedures and the general or regional anesthesia of the subject-patients. If your procedures will be performed at a UW Medicine facility or affiliate, the anesthesiologist must be a UW faculty member.

- ** If you checked the box about radio-isotopes: you are responsible for informing in advance all appropriate clinical personnel (e.g., nurses, technicians, anesthesiologists, surgeons) about the administration and use of the radio-isotope, to ensure that any personal safety issues (e.g., pregnancy) can be appropriately addressed. This is a condition of IRB approval.
- **10.4 Data and Safety Monitoring**. A Data and Safety Monitoring Plan (DSMP) is required for clinical trials (as defined by NIH), and for studies funded by or involving the Department of Justice. If required for your research, upload your DSMP to the **Supporting Documents** SmartForm in **Zipline**. If it is embedded in another document you are uploading (for example, a Study Protocol, use the text box below to name the document that has the DSMP.

We plan to use a Data Safety and Monitoring Board (DSMB) to review problems when reported, and then in aggregate for this project on an annual basis. These procedures will protect the safety of our research participants and ensure that our study procedures are not harmful in any way. Serious, unexpected adverse events related to mHealth intervention research participation are very rare in studies that are conducted by our group. The PI, in consultation with co-investigators and others as needed, will review Adverse Event reports. They will gather other information to investigate the event and determine the need for subsequent action including reporting to the IRB and if determined an adverse event by the IRB, will then be reported to the DSMB.

10.5 Un-blinding. If this is a double-blinded or single-blinded study in which the participant and/or you do not know the group to which the participant is assigned: describe the circumstances under which unblinding would be necessary, and to whom the un-blinded information would be provided.

N/A

10.6 Withdrawal of participants. If applicable, describe the anticipated circumstances under which participants will be withdrawn from the research without their consent. Also, describe any procedures for orderly withdrawal of a participant, regardless of the reason, including whether it will involve partial withdrawal from procedures and any intervention but continued data collection or long-term follow-up.

Participants will be withdrawn if we find they have previously enrolled in the study, used FOCUS or if they become unavailable for data collection over the 6 month participation (i.e. hospitalized or incarcerated).

10.7 Anticipated direct benefits to participants. If there are any direct research-related benefits that some or all individual participants are likely to experience from taking part in the research, describe them below:

Do not include benefits to society or others, and do not include subject payment (if any). Examples: medical benefits such as laboratory tests (if subjects receive the results); psychological resources made available to participants; training or education that is provided.

Participants may experience improvement in their illness management, psychosocial functioning, reduction in distress associated with psychiatric symptoms, and enhanced recovery. The potential benefit to future patients is that the study may provide data on effective implementation methods for improving outpatient illness management via mHealth. Community mental health stakeholders may benefit from the introduction of a new treatment approach that may improve patient outcomes, increase their access to timely and relevant information, and perhaps reduce the burden linked with in-person/clinic based care. Considering the minimal risks of the proposed research to outpatient and staff participants, and the potential benefit, the benefits of the research seem to far outweigh the risks.

(10.8) Individual subjects findings.

a. Is it likely that your research will discover unintentionally discover a previously unknown condition such as a disease, suicidal intentions, or genetic predisposition?

No Ye

ightarrow If yes, explain whether and how you would share the information with the subject.

There is a possibility of participants disclosing harmful intentions. If participants disclose suicidal or homicidal intention, research staff will probe for more details (i.e. if they have a plan, date, person of interest), and will deliberate with the lead PI (a trained clinical psychologist) the level of risk and if there is a need for clinical response. Unless there is an overt need for immediate care (i.e., participant said they would immediately hurt themselves or others, admitted to overdosing prior to meeting with research staff, etc). If elevation is deemed necessary by the research team, a member of the research staff would then reach out to their clinical team to proceed with the outlined protocol procedures of the local site (mental health clinic serving as a study site). If participants indicate a 1 or higher on Q9 of the PhQ9 Scale ("Thoughts that you would be better off dead, or of hurting yourself"), will be sent an email providing additional resources (please see 'Email for PHQ9' attachment in this modification).

b. Do you plan to routinely share the individual results of your study procedures with the subjects – such as genetic test results, laboratory tests, etc.?

x No Ye

→ If yes, complete and upload the SUPPLEMENT: Participant Results Sharing to the **Supporting Documents** SmartForm of **Zipline**

10.9 Commercial products or patents. If a commercial product or patent could result from this study, describe whether subjects might receive any remuneration/compensation and, if yes, how the amount will be determined:

Participants would not receive any compensation if a commercial product or patent were created. This is clearly stated in the consent form.

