The FOCUS application uninstalls at 3 months and then the 3 month web-based outcome assessment will be sent via text and will ask participants to complete it in a private and quiet space. Once again those who express difficulty completing the assessment through the web-based platform can request a call with an assessor on the research team. Participants who complete treatment will be mailed out a certificate of completion to their home address or clinic (based on participant's choice). They will no longer have access to the app, nor will participate in weekly calls for the next 3 months. They would then be sent another assessment at 6 months to complete.

Patient Participant Assessment:

Patient participants will receive a text from researchers just before their assessment date providing instructions on how to complete the online assessment. They will then be invited to conduct assessments at 0, 3, and 6 months via embedded link to a secure study portal (Qualtrics). For participants who need additional assistance, they can come into the participating clinic to complete on a tablet provided by the research team. Patient participants will receive \$30 compensation for each completed assessment (estimated completion time < 45 minutes) for a maximum of \$90 compensation (Plus additional \$10 each assessment to compensate data transmission or travel to site if more assistance is necessary). All participants will be paid for each assessment, but they will not be compensated for engagement in the intervention; assessments are administered to everyone enrolled in the study regardless of how/whether they engaged in FOCUS (note: all patient participants own working smartphones as part of inclusion criteria).

Assessments include questions about psychiatric treatment and hospitalizations, along with other measures of mental health including depression, anxiety, hearing voices, and recovery:

- Demographics and other characteristics
- PhQ9
- GAD-7
- Hospitalization- days hospitalized, no identifiers will be captured.
- ISI: Insomnia Severity Index
- Green Paranoid Thoughts Scale
- Symptom Checklist SCL-9Hamilton Program for Schizophrenia Voices Questionnaire (HPSVQ)
- Recovery Assessment Scale (RAS)
- Illness Management Recovery Scale (IMRS)
- Working Alliance Inventory (3M only)
- mHealth Mastery Measure (3M only)
- AIM
- Satisfaction

Information we plan to collect from EMR data:

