- **d.** Consent. Will you obtain consent now from subjects for the banking and/or future sharing?

Yes → If yes, be sure to include the information about this consent process in the consent form (if there is one) and in your answers to the consent questions in Section 6.

e. Withdrawal. Will subjects be able to withdraw their data/specimens from banking or sharing?

→ If yes, describe how, and whether there are any limitations on withdrawal.

Example: data can be withdrawn from the repository but cannot be retrieved after they are released.

f. Agreements for sharing or release. Confirm by checking the box that you will comply with UW (and, if applicable, UW Medicine) policies that require a formal agreement between you and the recipient for release of data or specimens to individuals or entities other than federal databases.

Data Use Agreements or Gatekeeping forms are used for data; Material Transfer Agreements are used for specimens (or specimens plus data. Do not attach your template agreement forms; the IRB neither reviews nor approves them

x Confirmed

5.9 Communication with subjects during the study. Describe the types of communication (if any) you will have with already-enrolled subjects during the study. Provide a description instead of the actual materials themselves.

Examples: email, texts, phone, or letter reminders about appointments or about returning study materials such as a questionnaire; requests to confirm contact information.

If technical issues are identified or if participants have gone 'dark' (missing data over a period of time) we will provide a text message or call checking in with the participant. Based on their response (i.e. express needing technical support, or non-response), an RA will contact the participant to ensure their phone is working and to assess if they are still interested in participating. If a participant has gone dark for in extended period of time and are unable to be reached by phone, a letter will be sent to their mailing address (email or physical mailing address: copy of letter attached). PHI will not be transmitted in text messages or emails.

5.10 Future contact with subjects. Do you plan to retain contact information for your subjects so that they can be contacted in the future?

No x Yes

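### The only explicit response to a PHQ-9 item 9 score of 1 or higher is a resource email; nothing in the protocol text routes a high score into the staff, lead-PI and clinic route described beside it

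*Protocol*

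**What the plan says.** Section 10.1, item 4, of the Protocol covers disclosure of harm to self or others and gives two responses with two triggers.

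- **Staffed route.** "If participants disclose suicidal or homicidal intention, research staff will probe for more details". They then weigh the level of risk with the lead PI, a clinical psychologist. If the team decides to escalate, research staff contact the participant's clinical team, who follow the local site's procedures.
- **Item 9.** "If participants indicate a 1 or higher on Q9 of the PhQ9 Scale", they "will be sent an email providing additional resources". The paragraph points to an attached email template.

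Section 10.8 repeats both responses. Item 2 of section 10.1 had already named the event as foreseeable: "Individuals may also endorse suicidal ideation when completing measures or bring this up during screenings or debriefings".

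Under section 5.1 the PHQ-9 is part of the patient assessment at 0, 3 and 6 months. The usual mode is a Qualtrics link completed alone. A telephone assessor or a tablet at the clinic is available to those who need help.

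**The concern.** The protocol foresees suicidal ideation being endorsed on a questionnaire, and it has a clinically led route for dealing with suicide risk. The item that measures ideation is nevertheless given its own response, which is an email. There is no higher tier, no named reviewer, no review time and no link to the staffed route.

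Patient safety is at stake. If staff follow the rule literally, a participant who gives the most severe answer on a web form gets the same email as one who scores 1. No stated step has a person read the answer, call the participant or tell the clinic.

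**Working it through.** No arithmetic applies. The check is whether any text connects an item 9 score to action by a person.

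**The two triggers**

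| | Staffed route | Item 9 rule |
|---|---|---|
| Trigger | Disclosed suicidal or homicidal *intention* | Score of 1 or higher on an item quoted as *thoughts* |
| First action | Staff question the participant | Resource email |
| Clinical review | Lead PI | None stated |
| Clinic contact | If the team judges it necessary | None stated |
| Graded by severity | Yes, by judgement | No, one threshold |
| Where stated | 10.1 item 4; 10.8 | 10.1 item 4; 10.8 |

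No sentence in either section joins the two columns.

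**Other text that might join them**

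1. *Section 9.1* offers to connect patients with clinical staff if needed, in the context of discomfort during assessments. It is the nearest statement, but it is general and names no score.
2. *Section 5.1, call before each assessment.* A call is planned before the 0-, 3- and 6-month forms. It comes before the answer is given, so it cannot respond to it.
3. *Section 5.1, facilitator meeting and weekly calls.* These follow the baseline form, but no text says that facilitators see PHQ-9 answers. The calls are described as using FOCUS data.
4. *Sections 1.8 and 5.1, clinician dashboard.* Follow-up here rests on self-assessments made in the app, not on the Qualtrics PHQ-9.
5. *Section 10.4, DSMB.* It covers reported problems and an annual aggregate review. It does not mention individual item scores.
6. *Section 5.1, telephone or tablet completion.* An assessor who hears the answer could treat it as a disclosure. That depends on mode and on judgement; it is not a stated rule.
7. *Sections 2.1, 2.2 and 4.1.* Participants are active clinic patients, and those planning to leave care within 6 months are excluded. This lowers the background risk, but nothing says the clinic learns of the answer.

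The SAP does not address item 9.

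**Result.** The item 9 rule appears in two places with the same single action. None of the seven provisions above is tied to an item 9 score. The missing link is the same at 0, 3 and 6 months.

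**The case against.** The best defence is that the email is additive. The item 9 sentence closes a paragraph on harm to self or others, straight after the staffed route, and speaks of additional resources. Nothing says that the email replaces the route, and an item 9 answer could itself be read as a disclosure. That reading is fair and may be what was meant. It does not settle the matter: the route is worded for *intention*, the item is quoted as *thoughts*, and a separate rule for item 9 would be an odd way of saying that every score of 1 or higher already calls for staff questioning.

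A second defence is that the steps may lie in documents we cannot see: the PHQ-9 email attachment, other uploaded documents including any separate data and safety monitoring plan, the printed study protocols mentioned in section 12.2, or the consent form. This stands, and it limits confidence.

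Three stronger readings are tempting but unsupported.

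- *That nobody would act on a high score.* The text omits the link; it does not forbid action.
- *That the gap is worse at 3 and 6 months.* Section 5.1 does say "The FOCUS application uninstalls at 3 months and then the 3 month web-based outcome assessment will be sent via text", and of participants after treatment, "They will no longer have access to the app, nor will participate in weekly calls for the next 3 months". But weekly calls are not an item 9 trigger at any time, so their end does not change the gap.
- *That section 5.9 rules out follow-up.* It says "we will provide a text message or call checking in with the participant" for technical problems or missing data. The section is plainly not a full list, since it also omits the PHQ-9 email and the calls before assessments. Its silence on item 9 shows nothing.

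**Conclusion.** The point holds as a missing link between a score and an existing safety route. The only explicit response to any item 9 score of 1 or higher is an email, and no visible text sends a high score to staff, the lead PI or the clinic. For a web-completed form at any of the three assessments, following the stated rule can leave a high score without human follow-up.

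The number of forms affected is unknown, because the documents give no endorsement rate. The conclusion assumes that the unseen documents do not already contain the step; if they do, only a cross-reference is missing. Confidence is medium for that reason. This is a cheap improvement on patient-safety grounds and does not affect the design or the analysis.

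**What to change.** 1. Keep the email for any score of 1 or higher.
2. Add to sections 10.1 and 10.8 that an item 9 score at or above a fixed level (for example 2 or higher, confirmed by the lead PI) triggers a Qualtrics alert to existing research staff. They start the questioning, lead-PI and clinic-contact route already described, within a fixed time (for example by the next business day).
3. Tell participants that survey answers are not monitored in real time and that high item 9 answers may be followed up, if the consent form does not already say so. Section 10.1, item 1, gives a similar warning about app content.
4. If an attachment or printed protocol already contains these steps, cite it in section 10.1 instead.

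The cost is a protocol modification, one survey alert and some time from existing staff. The volume is unknown without an endorsement rate, but a level above 1 cannot bring more forms for review than reviewing every score of 1 or higher. Section 5.4 keeps a key linking study IDs to contact details, so a flagged form can be traced.

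A separate drafting correction, which adds no weight to this point: the sentence that begins "Unless there is an overt need for immediate care" is unfinished in both sections and should state the immediate action.

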part of the CMHC clinical staff but hired and trained specifically for this role. 58 The clinical training materials and supervision structure was adapted and refined over the course of the 3-year study. The EF served as the point of contact, FOCUS trainer, and mHealth supporter for patients and staff. The facilitator met with participants at the beginning of the intervention to build rapport and to provide smartphone and FOCUS training. All other interactions were conducted remotely, successfully.

D. FOCUS: Multi-site deployment (pilot IF). With funding from the Center for Medicare and Medicaid Innovation (C1MS331052) FOCUS was used in conjunction with a treatment offered to people with SSD who were recently discharged from a psychiatric hospitalization. 59 This effort was conducted in partnership with CMHCs in eight states and constitutes the largest deployment of an mHealth intervention for people with SSD to date (n=342). 33 Clinical staff members at each site were selected and trained as internal practice facilitators to serve as the primary point of contact for patients, provided technical troubleshooting and smartphone configuration services, and served as the local mHealth champion and resource for treatment teams. 59, 60 Results were promising: Participants engaged with FOCUS on 82% of the weeks they had the smartphone and 44% used the intervention over 5-6 months, on average 4.3 days a week. Relevance for implementation: All study sites were able to identify personnel to serve as internal facilitators, all facilitators successfully completed training with our study team before commencing IF activities at their agencies, CMHC staff were able to log on, understand, and use the FOCUS clinical dashboard successfully. Notably, on-site CMHC personnel identified FOCUS candidates, and the vast majority of patients in the relapse prevention program who were offered FOCUS agreed to use it (92%). While the uptake and patient engagement findings were encouraging in terms of feasibility of the IF model, it was not structured as a controlled experimental study; there was no implementation comparator arm, it was impossible to isolate the mHealth-specific facilitator costs,

or to determine the relative impact of more resource-intensive internal facilitation on patient outcomes relative to EF.

1.9 Supplements. Check all boxes that apply, to identify Supplements you should complete and upload to the **Supporting Documents** SmartForm in **Zipline**.

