FOCUS has three elements: 1) FOCUS application (app): The system includes pre-programmed daily selfassessment prompts as well as on-demand functions that can be accessed 24 hours a day. Selfmanagement content was adapted from psychosocial intervention strategies targeting five broad domains: Voices (i.e., coping with auditory hallucinations via cognitive restructuring, distraction, guided hypothesis testing), Mood (i.e., anaging depression and anxiety via behavioral activation, relaxation techniques, supportive content), Sleep (i.e., sleep hygiene, relaxation, health and wellness psychoeducation), Social (i.e., cognitive restructuring of persecutory ideation, anger management, activity scheduling, skills training), and Medication (i.e., behavioral tailoring, reminders, psychoeducation). The system uses audio prompts, video content, cartoons, and written text to deliver coping strategies in the form of interactive questions, suggestions, and guided demonstrations. Content can be accessed as either brief video or audio clips or sequences of digital screens with written material coupled with visual displays; 2) Clinician dashboard: FOCUS users' responses to daily self-assessments are securely transmitted to a remote server. The information is processed and displayed on an online dashboard with a real-time summary of engagement, module selection, and reported symptom severity over the last 30 days, that is accessible to authorized staff who use it to inform and enhance their clinical services. If, dashboard data suggest a patient requires additional assistance, staff call to assess further and provide consultation; 3) mHealth support personnel: FOCUS patients are engaged throughout the treatment period by trained individuals to encourage their adherence to FOCUS by assisting them in all technical and clinical aspects of the intervention.

FOCUS data will be used directly by the IF / EF to inform their weekly calls with participants. A summary of FOCUS data use may also be shared with their clinicians to inform their care / treatment plans. Weekly phone calls will be used to assess if there are any technical issues experienced by the participant, along with resolving that issue. IF/EF's will also talk about the FOCUS app use over the previous week and how they can use the tips/ strategies to support their goals. Each weekly call should last approx. 10-15 minutes.

Study Sites

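### Safety review in section 10.4 depends on reported events; hospitalization and PHQ-9 item 9 are collected but not counted as safety outcomes, so a zero count of reports would not show a low harm rate

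*Protocol*

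**What the plan says.** **Safety review (protocol 10.4).** The monitoring board will "review problems when reported, and then in aggregate for this project on an annual basis". On individual events, "The PI, in consultation with co-investigators and others as needed, will review Adverse Event reports"; the team investigates, decides on reporting to the IRB, and passes the event to the board if the IRB determines that it is an adverse event. The section gives no definition of an adverse event, no solicited question and no collection window. It nevertheless says that these procedures will make sure the study does no harm of any kind.

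**Data collected (5.1, Patient Participant Assessment).** The 0-, 3- and 6-month list includes the PHQ-9 and "Hospitalization- days hospitalized, no identifiers will be captured". Under 10.1 (item 4) and 10.8, a score of 1 or higher on PHQ-9 item 9 leads to an email with resources. Disclosed suicidal or homicidal intent is probed, discussed with the lead investigator and may be passed to the clinic.

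**Named risk (10.1, item 1).** "The main risk is engaging in intervention content while engaged in other activities that require participants' full attention". The stated response is an instruction to use the phone only when safe.

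**Calls (5.1).** "Weekly phone calls will be used to assess if there are any technical issues experienced by the participant". The other stated topics are app use over the past week and how its strategies support the patient's goals.

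**Lost contact and withdrawal (5.9, 10.6).** A silent participant gets a text or call, then contact from a research assistant; if still "unable to be reached by phone, a letter will be sent to their mailing address". Participants unavailable for data collection, with hospitalization and incarceration as the examples, are withdrawn. The form asks about continued data collection after withdrawal; the answer describes none.

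**SAP.** It covers Aims 1 to 3 and power. It has no safety analysis and does not mention hospitalization or item 9.

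**The concern.** The issue is what becomes an event in the first place. Protocol 1.8a names psychiatric hospitalization, self-injury and suicide among the consequences of poorly managed illness. The study asks every patient about hospital days and, through item 9, about thoughts of death or self-harm. No text carries those answers into the board's aggregate, and no text says how an accident while using the app would come to light unless someone mentioned it.

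At stake is the meaning of the safety statement at the end of the trial. If the count of adverse event reports is zero or very low, the board and later readers may take it as evidence of safety when it may reflect only how events were sought. It would not support the assurance given in 10.4. Withdrawing patients who are in hospital could also remove relevant cases from the data set.

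**Working it through.** The documents give no expected event rate, detection probability or safety power, so there is no stated figure to reproduce. The check has two parts.

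**1. Does collected information reach safety review?**

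- Hospital days: collected at 0, 3 and 6 months (5.1). Not mentioned in 10.4 or the SAP, and not among the patient outcomes named in Aim 3 (1.5).
- Item 9: collected at the same times and acted on by email (10.1, 10.8). No count or event record is described.
- Main risk: met by instruction (10.1). Not in the listed measures or call topics (5.1).
- Hospitalized or incarcerated: a reason for withdrawal (10.6). Not linked to 10.4.

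**2. What would a zero count of reports show?**

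Inputs: n = 300, from 20 clinics × 15 patients (5.1) and from 20 × 5 clinicians × 3 patients (SAP, Power Analysis). Let p be the true proportion harmed and s the share of harms that become reports. Neither is in the documents, so both are assumed over a range.

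The chance of no reports is (1 − p·s)^300:

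| True rate p | s = 100% | s = 25% | s = 10% |
|---|---|---|---|
| 1% | 4.9% | 47% | 74% |
| 2% | 0.2% | 22% | 55% |
| 5% | <0.1% | 2.3% | 22% |

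For example, p = 2% and s = 25% give (1 − 0.005)^300 = 0.22.

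The one-sided 95% upper bound on p after zero reports is [1 − 0.05^(1/300)]/s = 0.99%/s:

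- s = 100%: 1.0%
- s = 50%: 2.0%
- s = 25%: 4.0%
- s = 10%: 9.9%
- s = 5%: 19.9%

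These bounds ignore clustering. If the SAP's between-organization ICC of 0.19 applied to harms (an assumption), the design effect would be 1 + 14 × 0.19 = 3.66, the effective n would be 300/3.66 = 82, and the bound at s = 100% would be 3.6%.

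**Arms, spontaneous reports only.** Internal facilitators are clinic staff who may meet patients in person; external facilitators are university staff (5.1). Assume 150 patients per arm, the same true rate of 10%, and s of 50% against 25%. Expected reports are then 150 × 0.10 × 0.50 = 7.5 and 150 × 0.10 × 0.25 = 3.75, a twofold difference with no difference in harm.

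**The case against.** The strongest reply is that ascertainment is not wholly passive. Every patient is asked about hospital days and item 9 at three time points through the same portal, disclosed intent is probed, and dashboard data can prompt a staff call. This stands in part: the data exist and could be tabulated by arm. But the plan does not say that they will be, and the described responses are clinical ones with no link to event counting. The limit on inference therefore applies to a count of adverse event reports, not to everything the trial collects.

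A second reply is that absence is not proven. The form calls for a monitoring plan and data collection forms to be uploaded, and section 12.2 mentions printed study protocols. None of these is in the documents supplied. That stands and limits the finding, although the answer in 10.4 names no other document.

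Third, the arm comparison is weak ground: assessments are identical in both arms and the SAP plans no comparison of adverse events. That also stands, so the point on arms goes no further than spontaneous reports.

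A reader might also infer from the protocol's history that harms were missed before. Section 10.1 says "We have deployed FOCUS for periods ranging five days to seven months and have not had any adverse events reported", and section 1.8b describes 342 people "recently discharged from a psychiatric hospitalization" who used FOCUS. The documents do not support that inference. The statement sits under risks of the intervention and speaks of events reported; it does not claim that nobody was hospitalized for any cause, and how events were captured in that deployment is not described. For the same reason section 10.1 needs no rewording. Nor do the documents give a hospitalization rate from which to project how many events this trial would leave uncounted.

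**Conclusion.** The concern holds in a limited form. As described in the documents supplied, safety review starts from reports. Hospitalization and item 9 are collected from all patients but not counted as safety outcomes, the named main risk is not in the listed measures or described call topics, and hospitalized patients can be withdrawn. A zero count of reports could not separate a low harm rate from low ascertainment: with 300 patients the upper bound is about 1% if every harm is reported, 4% if a quarter are, and 9.9% if a tenth are. The true rates, the reporting shares, the equal split of patients between arms and the use of the ICC for harms are assumptions; the sample size and the ICC value come from the documents.

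It would be too strong to say that these data are never counted at all, or that any safety finding from the trial would be worthless. Both arms receive FOCUS, so even complete counts would describe harms without an unexposed comparator.

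**What to change.** Amend section 10.4 as follows.

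1. For each annual board report, tabulate by arm any hospitalization and any item 9 score of 1 or higher (the protocol's own threshold) from the 3- and 6-month assessments. Show the number assessed, and beside it the number withdrawn or lost by known reason: hospitalized, incarcerated, other, unknown. Use only information the study already obtains. Asking clinics for new patient-level details should not be part of this, because section 5.6 says the study no longer plans to capture health information that needs signed authorization.
2. Add one harm question, worded identically in both arms, to the 3-month assessment and, if feasible, to the weekly call script. It should cover accident or injury while using the app, distress from it, and a lost or stolen phone. Enter answers in one central log.

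If a separate monitoring plan or call script already does this, a reference to it in 10.4 is enough.

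The cost is a protocol modification, one survey item, one call-script line and one table from planned data, with no extra staff. The downside is a few extra minutes per patient and a reported harm count that may be above zero.
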